Participating patients will be randomly assigned to video headset analgesia (video headset featuring a relaxation program with three dimensional video experience and binaural audio) or sham video headset (identical video headset mimicking a void theater where a 2D content will be displayed on a “ virtual screen” in front of the user). The headset will not be labeled with the terms “VR,” “virtual reality,” or “Pico.” The study will be performed at two Cleveland Clinic hospitals.

Pico G2 4K VR goggles (left) and a sample image of the video headset analgesia software displayed (right)

Virtual Reality Distraction for Reduction in Acute Postoperative Pain

[figure not shown]

Diagram of the sham video mimicking a void theater with a screen showing 2D content (left) and a sample image of the sham video headset displayed (right)

B. Setting and Population

Inclusion criteria:

- (1) Written informed consent;
- (2) Men or women 18-85 years old;
- (3) American Society of Anesthesiology Physical Status 1-3;
- (4) Scheduled for elective, primary total hip arthroplasty;
- (5) Anticipated hospitalization of at least 1 night;
- (6) Expected to require parenteral opioids for postoperative pain;
- (7) Able to use IV PCA systems.

Exclusion criteria:

- (1) Use of more than 30 mg/day of oral oxycodone (or equivalent);
- (2) Greater than 12 weeks of current and continued opioid use;
- (3) History of seizures, epilepsy, motion sickness, stroke, dementia;
- (4) Non-English speaking;
- (5) Women who are pregnant or breastfeeding;
- (6) History of illicit substance use disorder.

C. Withdrawal Criteria

Patients are free to withdraw from study at any time. Patients will also be removed from

Virtual Reality Distraction for Reduction in Acute Postoperative Pain

study at any time for adverse events or if deemed necessary for their safety. Patients should be asked if they want to fully withdraw from the study, or only stop the intervention and answer the surveys and allow collect other data that may apply.

D. Protocol

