Patients will be randomized to either sham video headset group or video headset analgesia group. Study coordinators will be assigned to either randomize and program headsets, or to assess patients' during sessions. All enrolled patients will receive education by research team who will demonstrate how to adjust the headset strap, activate the device, and adjust the volume following a predetermined script with the goal of making patients feel comfortable using the device on their own. Patients will be assured they will receive the routine pain control in addition to video headset experience.

Anesthetic management will follow pre-established clinical and institutional guidelines. Anesthesia will be at attending anesthesiologist's discretion; usually that will be spinal anesthesia without intrathecal opioids. Intraoperative and postoperative opioids will also be given at the discretion of the attending anesthesiologist. Prophylactic antibiotics will be given per surgical routine. Other intraoperative and postoperative medications may be used and include anti-inflammatory medications, gabapentin, pregabalin, ketamine, or lidocaine patches. Clinicians will be encouraged to give a single dose of dexamethasone (4-8 mg) for PONV prophylaxis. Inhaled steroids will be permitted as necessary to treat reactive airway disease.

Patients will be randomized in a 1:1 ratio to either relaxation program the morning of the first postoperative day, before start the intervention. Randomization will be based on computer-generated codes with random blocking and no stratification. Allocation will be concealed by a web-based system. The use of the video headset will be offered postoperatively while patients are awake between 8 AM to 4 PM. **Each session will have a maximum duration of 8 minutes. We will target 3 session per day, with at least one hour separating each treatments.** Treatments will continue for two postoperative days or until hospital discharge, whichever comes first.

The study device is a Pico G2 4K headset, but all labels will be masked to reduce

Virtual Reality Distraction for Reduction in Acute Postoperative Pain

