electronic medical records for opioid consumption in PACU and ward; pain scores before surgery, in PACU and ward; requirement of oxygen in PACU and ward; nausea and vomiting, requirement of antiemetics, requirement of naloxone, and adverse events. Patient interaction with presented video content will be characterized using eye-tracking metrics.

Outcomes

All postoperative assessment will be made by an investigator who is strictly blinded to treatment allocation, and actual treatment (e.g., full immersion or sham distraction).

Primary Outcome

1. **Pain Scores.** We will assess pain using NRS scores (0-10, with 10 being worst) immediately before and 15 minutes after each intervention with the device, starting on postoperative day one (POD1) and until end of postoperative day two (POD2) or hospital discharge, whichever occurs first.

Secondary Outcomes

1. **Total opioid consumption.** We will measure total opioid consumption, converted to morphine milligram equivalents (MME), starting at the first pre-intervention pain score measurement, postoperative day one (POD1), and until the end of postoperative day 2 (POD2) or hospital discharge, whichever occurs first.
2. **Pain scores.** We will capture all pain score measurements done every 4 hours by standard of care starting at the first pre-intervention pain score measurement, POD1, and end of postoperative day two or hospital discharge, whichever occurs first, using NRS scores (0-10, with 10 being worst). Only the pain scores from routine nurse assessments will be used here (pain scores measured as a part of the primary outcome won't be included).
3. **Perception of video system usability.** Patient's perception of video system

Virtual Reality Distraction for Reduction in Acute Postoperative Pain

usability will be assessed using a validated questionnaire (System Usability Scale¹³) once after the last intervention with the device and before hospital discharge. The System Usability Scale is scored from 0 to 100 and higher scores are related with devices that are easier to use.

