4. **Post discharge pain outcomes.** Patients will be called one week after hospital discharge to assess post discharge pain outcomes using a validated questionnaire (Pain Outcomes Questionnaire Short Form¹⁴) which evaluates five domains (pain, mobility, activities of daily living, vitality, negative affect and fear). The Pain Outcomes Questionnaire Short Form is scored from 0 to 190 and higher scores are related with worst pain outcomes.

Tertiary Outcomes

1. **Anti-emetic medications.** We will record use of anti-emetic medications, and the outcome variable will be calculated as the number of anti-emetic medications administered starting at the first pre-intervention pain score measurement, POD1, until end of postoperative day two or hospital discharge, whichever occurs first.
2. **Patient mobility score.** We will measure patient mobility using physical therapy daily postoperative assessment (“6 Clicks” Basic Mobility Inpatient Short Form questionnaire¹⁵) starting at the first pre-intervention pain score measurement, POD1, until end of postoperative two or hospital discharge, whichever occurs first. The “6 Clicks” Basic Mobility Inpatient Short Form questionnaire is scored from 6 to 24 and higher scores are related with lower levels of functional impairment.

F. Data Analysis

We will assess the balance between randomized groups on baseline variables using the standardized difference (i.e., difference in means or proportions divided by the pooled standard deviation). For all analyses we will adjust for baseline variables having absolute standardized difference <0.10 ¹⁶. The analyses will be carried out using a modified Intention-to-Treat approach. More specifically, all patients who receive the treatment for

Virtual Reality Distraction for Reduction in Acute Postoperative Pain

any duration of time will be included in the analysis. For example, if a patient chose to withdraw on POD 2, their measurements from POD1 would still be used in the analysis. We'll only exclude patients who didn't receive any treatment at all either due to refusal or because they chose to withdraw.

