Primary outcome. We will assess the effect of VR on NRS pain score after each study treatment over postoperative days one and two using a linear mixed effects model on the series of post-VR pain scores while adjusting for the corresponding pre-VR pain score, with time and randomized group as fixed effect categorical variables. We will adjust for within-subject correlation across the pain scores using either an autoregressive AR (1) or unstructured correlation matrix, whichever has better fit (lower AIC, BIC). We will assess the group-by-time interaction, but even if significant ($P < 0.15$) the primary result will be made collapsing over time.

Secondary Outcomes

1. **Total opioid consumption.** We will assess the effect of VR on log-transformed total opioid consumption starting at the first pre-intervention pain score measurement, POD1, and until end of postoperative day 2 or hospital discharge, whichever occurs first, using a linear regression model.
2. **Pain scores.** We will assess the effect of VR on pain score over time starting at the first pre-intervention pain score measurement, POD1, and until end of postoperative day 2 or hospital discharge, whichever occurs first, using a linear mixed effects regression to account for within-subject correlation. Only the pain scores from routine nurse assessments will be used here (pain scores from Aim 1 won't be used).
3. **Perception of video system usability.** We will assess the effect of VR on perception of video system usability as measured by the System Usability Scale using a Wilcoxon rank-sum test and report the median difference (along with the 95% CI) estimated using the Hodges-Lehmann approach.
4. **Post discharge analgesia.** We will assess the effect of VR on analgesia scores one week after discharge using a Wilcoxon rank-sum test and report the median

Virtual Reality Distraction for Reduction in Acute Postoperative Pain

difference (along with the 95% CI) estimated using the Hodges-Lehmann approach.

Tertiary Outcomes

5. **Anti-emetic medications.** We will assess the effects of VR on the number of times a patient required anti-emetic medication within starting at the first pre-intervention pain score measurement, POD1, and until postoperative day 2 or hospital discharge, whichever occurs first, using a Wilcoxon rank-sum test, and report the median difference (along with the 95% CI) estimated using the Hodges-Lehmann approach.

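### Two hospitals, unstratified randomisation and no hospital term in any model: a small, cheaply avoidable loss of precision, mainly for opioid use and nurse-recorded pain

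*Combined protocol and SAP*

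**What the plan says.** Section 3.A (Study Overview) gives the setting: "The study will be performed at two Cleveland Clinic hospitals".

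Section 3.D (Protocol) describes background care: "Anesthetic management will follow pre-established clinical and institutional guidelines", and "Intraoperative and postoperative opioids will also be given at the discretion of the attending anesthesiologist". It also permits several optional co-analgesics. On allocation it says "Patients will be randomized in a 1:1 ratio to either relaxation program the morning of the first postoperative day", and then "Randomization will be based on computer-generated codes with random blocking and no stratification".

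Section 3.E (Measurements) lists the demographic, medical-history, intraoperative and day-of-surgery variables. The day-of-surgery baseline comes from "electronic medical records for opioid consumption in PACU and ward; pain scores before surgery, in PACU and ward", among other items. Hospital is in none of these lists.

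Section 3.F (Data Analysis) specifies the primary mixed model on post-session scores "while adjusting for the corresponding pre-VR pain score, with time and randomized group as fixed effect categorical variables". The log-opioid regression and the mixed model for routine nurse pain scores name no baseline covariate. The remaining outcomes use Wilcoxon rank-sum tests. One general rule covers covariates: "For all analyses we will adjust for baseline variables having absolute standardized difference <0.10". No analysis mentions hospital.

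**The concern.** Background analgesia is a main outside determinant of opioid use, antiemetic use and routine pain scores. If practice differs between the hospitals, part of the variation in these outcomes belongs to hospital, and the design and models could remove that part at almost no cost. The plan does not remove it at randomisation, and no model removes it afterwards.

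The general covariate rule does not fill the gap. Hospital is not a listed baseline variable. Even if it were treated as one, the rule as printed adjusts for variables whose standardized difference is below 0.10, so it would leave hospital out exactly when hospital was imbalanced.

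Opioid consumption is the outcome most exposed. It is a total that stops at the end of postoperative day 2 or at discharge, so a hospital difference in either prescribing or discharge timing would feed into it.

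**Working it through.** **Inputs from the documents.** Two hospitals; 1:1 allocation; difference to detect 1 NRS point; SD 1.5; two-sided alpha 0.05; power 90%; 98 patients (49 per group), raised to 113 for four analyses.

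**Inputs assumed.** The documents give neither the hospital split nor any hospital difference. Splits of 50/50, 70/30 and 80/20 are used, with a range of differences.

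**1. The plan's own figure.** n per arm = 2(1.96 + 1.2816)² × 1.5² / 1² = 47.3, rounded up to 48. The t-test version gives 48.3, rounded up to 49, hence 98 in total. A four-look gamma-family design (alpha gamma −4, beta gamma −1, non-binding futility) has an inflation factor of 1.132, and 98 × 1.132 = 111, within 3% of 113. The sample size reproduces.

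**2. Chance imbalance.** The SD of the between-arm difference in hospital share is √(4p(1−p)/N). With p = 0.5 and N = 113 this is √(1/113) = 0.094, so the 95% range is ±0.18. Simulation of unstratified 1:1 splits gives the same SD. The difference exceeds 10 percentage points in about 26% of trials and 20 points in about 4%. The standardized difference for hospital exceeds 0.10 in about 56% to 61% of trials across the three splits.

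**3. Imbalance relative to the standard error.** Take equal hospitals and an assumed difference of d = 0.5 SD. The 95% limit of the shift is 0.5 × 1.96/√N, and the standard error of the treatment effect is 2/√N (both in SD units).

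| N | Shift | SE | Shift / SE |
|---|---|---|---|
| 28 (first look) | 0.185 | 0.378 | 0.49 |
| 113 (final) | 0.092 | 0.188 | 0.49 |

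√N cancels, so the ratio is the same at every look.

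**4. Share of variance.** With equal hospitals and d in within-hospital SDs, the share is 0.25d²/(1 + 0.25d²). Removing it multiplies the confidence-interval width by 1/√(1 + 0.25d²).

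| d (assumed) | Variance share | CI narrower by |
|---|---|---|
| 0.3 | 2.2% | about 1% |
| 0.5 | 5.9% | about 3% |
| 0.8 | 13.8% | about 7% |

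**5. Power for the primary outcome.** Let D be the hospital difference in post-session pain that remains after pre-session adjustment. Omitting hospital adds D²p(1−p) to the variance. Power = Φ(1/(σ√(2/49)) − 1.96), for the fixed design with 49 per arm; at σ = 1.5 it is 0.910. Ranges cover the three splits.

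| D (NRS, assumed) | If 1.5 includes hospital: power with hospital in the model | If 1.5 is within hospital: power with hospital omitted |
|---|---|---|
| 0.25 | 0.911–0.912 | 0.908–0.909 |
| 0.5 | 0.915–0.917 | 0.902–0.905 |
| 1.0 | 0.928–0.938 | 0.879–0.890 |

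Against 0.910, power moves by less than 1 point for D up to 0.5 and by about 2 to 3 points at D = 1.0, where hospital is 7% to 11% of 1.5².

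**6. Secondary outcomes.** The documents give no SD for log opioid consumption or nurse-recorded pain, so no power figure can be calculated. Step 4 is the only guide.

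**The case against.** The case against is substantial.

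- **The hospital difference is not documented.** The protocol does not say that the two hospitals' guidelines differ, and both belong to one health system. Discretion lies with the individual anesthesiologist, and that variation within a hospital survives any hospital adjustment. All of this stands, and it is why every size above is conditional.
- **The plan already collects closer measures of background analgesia.** Intraoperative, PACU and ward opioid use and day-of-surgery pain are recorded as baseline, largely before randomisation on the first postoperative morning, and the covariate rule makes them candidates in all analyses. This stands in part. Their use depends on observed balance under a rule that, as printed, drops the imbalanced ones. They also describe the day of surgery, while opioids remain discretionary during the outcome window.
- **The primary model adjusts for pre-session pain.** This stands: the adjustment should absorb much of any background difference.

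Two stronger readings are tempting. A reader might infer that the interim looks are especially exposed, because imbalance in hospital mix is widest at about 28 patients. Step 3 shows otherwise: the shift shrinks at the same rate as the standard error. A reader might also count the chance shift and the unexplained variance as two harms. They are one: with hospital out of the model its variance is already in the residual, so the shift is ordinary sampling noise covered by the nominal error rate.

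**Conclusion.** The point holds as a minor matter of precision. Two hospitals, discretionary co-analgesia, unstratified allocation and the absence of hospital from every baseline list and model are all in the text. Nothing in the documents supports a reading that the comparison is biased or the type I error inflated.

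For the primary outcome the gain is under 1 point of power unless the residual hospital difference approaches 1 NRS point. For total opioid consumption and nurse-recorded pain it may be larger, with about 2% to 14% of the variance removed under assumed differences of 0.3 to 0.8 SD and hospitals of equal size.

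The reversed direction of the 0.10 covariate rule is a separate and larger defect. Correcting it alone would not guarantee that hospital enters the models, because hospital is not a listed baseline variable.

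**What to change.** Before the first interim look, amend section 3.F to include hospital as a fixed effect, regardless of observed balance, in three models: the primary mixed model, the nurse-pain mixed model and the log-opioid regression. If recruitment has not begun, also set the web-based system to stratify by hospital, with random blocks within each hospital. If it has begun, the fixed effect alone is sufficient.

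Hospital-stratified rank tests (van Elteren) are optional. If adopted, they need a matching stratified Hodges-Lehmann estimate and interval, since the plan reports that estimate with each rank-sum test.

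The cost is one degree of freedom per model, one system setting and a sentence of SAP text. Clinical care does not change, and variation between clinicians within a hospital remains.

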the risk of unblinding. A member of the research team will program the headsets to either one of the two different relaxation programs and will explain to patient how to set up and use the device. The sham video group will watch a 2D conventional video projected in a virtual screen mimicking a void theater in the same headset, whereas the treatment group will have a full immersive experience with three-dimensional video and binaural audio. Other research team members and healthcare providers will be blinded to intervention assignment and pain assessment will be done by the blinded study coordinator. Patients will not use the video headset device during physical therapy or while ambulating and use of the headset will be restricted to the hospital.

Patients will be allowed to receive prophylactic anti-emetics during intraoperative time based on the risk assessment for nausea and vomiting. Postoperative anti-emetics for symptomatic treatment will also be allowed; ondansetron will be the first choice.

Patients will be followed-up by phone call one week after hospital discharge to ask them the Pain Outcomes Questionnaire Short Form (POQ-SF). No more than 3 attempts should be accomplished to contact the patients for the one-week post-discharge follow-up.

E. Measurements

Demographic and Background Information

Demographic data to be obtained includes height (cm), weight (kg), age (years), sex, ASA physical status classification, and self-declared ethnicity. Patients will be questioned for social history (tobacco) and medical history (pulmonary disease, kidney disease, diabetes mellitus, neurological disease, chronic pain conditions, illegal drug usage, alcohol abuse, myocardial infarction, previous surgery or stent placement and medications usage). Available preoperative laboratory tests and medication list will be recorded.

Standard anesthesia monitoring will be used. Data obtained from electronic medical records for intraoperative variables will include: duration of surgery, intraoperative opioid consumption and antiemetic medications.

Data for variables for the day of surgery as a baseline will be obtained from

Virtual Reality Distraction for Reduction in Acute Postoperative Pain

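### Baseline record data are defined for the day of surgery and the matching outcomes start at the first POD1 session, so overnight opioid use and routine pain before randomisation may fall in neither window

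*Combined protocol and SAP*

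**What the plan says.** Section 3.E (Measurements, Demographic and Background Information) sets the perioperative baseline: "Data for variables for the day of surgery as a baseline will be obtained from" "electronic medical records for opioid consumption in PACU and ward; pain scores before surgery, in PACU and ward". The list continues with oxygen need, nausea and vomiting, anti-emetics, naloxone and adverse events. No clock time marks the end of the day of surgery.

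The outcome windows in Section 3.E begin later:
- Routine nurse pain: "We will capture all pain score measurements done every 4 hours by standard of care starting at the first pre-intervention pain score measurement", on POD1.
- Total opioid consumption has the same starting point.
- Anti-emetic use is "the number of anti-emetic medications administered starting at the first pre-intervention pain score measurement, POD1" onward.

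Section 3.D (Protocol) fixes the surrounding times. "Patients will be randomized in a 1:1 ratio to either relaxation program the morning of the first postoperative day, before start the intervention". Sessions are offered "while patients are awake between 8 AM to 4 PM".

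Section 3.F (Data Analysis) checks balance on baseline variables by standardized difference and makes adjustment depend on a threshold of 0.10. The log-opioid regression names no pre-treatment opioid covariate, and the routine-pain mixed model names no baseline pain score. The primary model does adjust for the score taken before each session.

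**The concern.** Read literally, opioid doses, anti-emetic doses and 4-hourly nurse scores recorded on POD1 before the first session are neither baseline nor outcome. Randomisation takes place that morning, so data recorded before it cannot have been affected by allocation and are valid baseline. For opioid use they are also the values nearest to the outcome window.

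Opioid reduction is a stated secondary hypothesis (Section 2, with a 25% reduction considered clinically important), and Section 1.1.E gives the absence of opioid data in earlier studies as part of the rationale. With the windows as written, a chance difference between arms in overnight opioid use would not appear in the balance table and could not trigger adjustment. A covariate that could narrow the confidence interval for the opioid effect would go unused. The missing clock time adds a practical problem: two people extracting the same records could reasonably produce different baseline totals.

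**Working it through.** The plan gives no figure for the length of this interval, so there is none to reproduce. Its sample size is set on the primary outcome. With SD 1.5, difference 1, two-sided alpha 0.05 and 90% power, the normal formula 2(1.960 + 1.282)² × 1.5² / 1² gives 47.3, so 48 per arm. The two-sample t version gives 49 per arm (power 0.904, against 0.898 with 48), which matches the stated 98. Nothing below changes it.

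**Length of the interval.** Inputs: session hours of 8 AM to 4 PM, morning randomisation, sessions of at most 8 minutes, a target of three a day at least one hour apart (all Section 3.D). Assumptions: the day of surgery ends at midnight, and randomisation falls between 8 AM and noon.
- First session at 8 AM: 8 h.
- First session at noon: 12 h.
- Latest first start that fits three sessions: 3 × 8 + 2 × 60 = 144 min = 2.4 h; 16 − 2.4 = 13.6 h, i.e. 13:36.
- Latest start for one full session: 15:52, or 15.9 h.

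Only time before randomisation counts as pre-randomisation baseline, and randomisation is in the morning, so the recoverable part is about 8 to 12 h. At one routine score every 4 h, that is 8/4 = 2 to 12/4 = 3 scores, plus all opioid doses in that time.

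**Value of a pre-treatment opioid covariate compared with none.** If it correlates r with the log outcome, residual variance is multiplied by 1 − r² and interval width by √(1 − r²). The documents give no r.

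| r (assumed) | variance factor | CI width factor |
|---|---|---|
| 0.3 | 0.91 | 0.95 |
| 0.5 | 0.75 | 0.87 |
| 0.7 | 0.51 | 0.71 |

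**Value of the overnight part on top of day-of-surgery use.** Simulation of 200,000 patients in 4-hour blocks: three on the day of surgery, two overnight, nine in the outcome window. Log opioid intensity is a patient effect plus an AR(1) term, with gamma noise. Information gain = (1 − R² without overnight)/(1 − R² with overnight) − 1. With gamma shape 2:

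| patient SD, AR SD, rho | R² day of surgery | R² with overnight | gain |
|---|---|---|---|
| 0.6, 0.6, 0.8 | 0.35 | 0.45 | 0.65/0.55 − 1 = 18% |
| 0.4, 0.7, 0.85 | 0.22 | 0.33 | 0.78/0.67 − 1 = 16% |
| 0.7, 0.4, 0.8 | 0.53 | 0.61 | 0.47/0.39 − 1 = 21% (23% unrounded) |

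The result depends strongly on the noise shape. In the same three settings, shape 0.5 gives about 6% to 10%, shape 1 gives 11% to 17%, and shape 4 gives 20% to 26%. Smaller SDs with weaker correlation (0.3, 0.3, 0.5) give 1% at shape 0.5 and 8% at shape 2. The overall range is about 1% to 26%, equivalent to interval widths multiplied by 1/√1.01 = 0.995 down to 1/√1.26 = 0.89.

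At shape 2, overnight use alone predicts about as well as day-of-surgery use alone (R² 0.38 against 0.35, 0.29 against 0.22, 0.50 against 0.53), from 8 hours instead of 12.

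**The case against.** **Wording, not data loss.** The plan never says that the day of surgery ends at midnight, and the baseline list includes opioid use and pain on the ward, which could be read as running to POD1. This stands as a limit on the claim. It does not remove the need for a stated end, because the plan supports either reading.

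**The most relevant baseline is still there.** A reader might infer that the best baseline is lost altogether. For pain, the documents show otherwise: a score is taken immediately before every session, the primary model uses it, and the first of these scores precedes any treatment and is closer to it than any overnight nurse score. What remains uncovered is record-based opioid and anti-emetic use and the routine nurse scores.

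**No bias.** A reader might infer that the comparison is distorted. It is not: both arms have the same windows, and chance imbalance is already reflected in the standard errors.

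**Overstated size.** A gap of up to 16 h is only the edge of the session hours and fits poorly with morning randomisation and three sessions. A gain of 16% to 23% holds for one undocumented noise shape. Neither should be relied on.

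**Spinal block.** It is tempting to argue that residual block masks day-of-surgery opioid use, since "usually that will be spinal anesthesia without intrathecal opioids". The documents give no block duration, so the point does not rest on this.

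**Moving the window alone gains nothing.** This is correct. The opioid model names no baseline opioid covariate, and the anti-emetic outcome is analysed by a Wilcoxon test without covariates. Precision improves only if adjustment is prespecified.

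**Outcome start.** Starting outcomes at the first pre-session score is consistent with an analysis set restricted to treated patients. Starting them at randomisation would be a preference, not a correction.

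**Conclusion.** The point holds as a minor one. Under the midnight reading, about 8 to 12 h of pre-randomisation record data, with two to three routine pain scores and all opioid doses in that time, are assigned to no window. They cannot enter the balance check or any adjustment. The consequence is lost precision and an incomplete balance check for the secondary opioid and routine-pain outcomes. The primary analysis and the sample size are untouched, and the treatment comparison is not biased.

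The size rests on inputs that the documents do not supply: where the day of surgery ends, when patients are randomised, and how strongly overnight use predicts later use. Over the simulated inputs, the added information on log opioid total is about 1% to 26%, and it is obtained only if the overnight value is in the model.

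**What to change.** **Section 3.E, baseline.** Run the record extract from the end of surgery to randomisation on POD1, in clock time. Report overnight opioid use (MME per hour) and the last routine pain score before randomisation as separate variables in the balance table.

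**Section 3.F, secondary outcomes 1 and 2.** Name overnight opioid use as a prespecified covariate in the log-opioid regression, stating its scale and how zero use is handled. Name the last pre-randomisation routine pain score as a covariate in the routine-pain mixed model. Include both whatever the observed standardized difference.

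The outcome windows can stay as written. Any interval between randomisation and the first session would remain outside both windows; it is short if the first session follows promptly.

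**Cost.** A wider date-time filter on data already in the electronic record, a few lines of text, and one degree of freedom per model. There are no new assessments, no patient burden and no change in sample size.
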